2.2 DISPOSITION OF PATIENTS

This section describes patient disposition for both patient study status and the patient analysis populations.

Screened patients are defined as any patients who signed the informed consent.

Randomized patients consist of all patients with a signed informed consent form who have had a treatment kit number allocated and recorded in the IVRS/IWRS database, regardless of whether the treatment kit was used.

For patient study status, the total number of patients in each of the following categories will be presented in the clinical study report using a flowchart diagram or summary table by treatment arm and overall:

- Screened patients
- Screen failure patients and reasons for screen failure
- Non-randomized but treated patients
- Randomized patients
- Randomized but not treated patients and reason for not being treated
- Randomized and treated patients
- Patients who completed the study treatment period, and patients who did not complete the study treatment period
 - Patients are considered having completed the 52-week blinded treatment period if they received the investigational medicinal product until the day before the Week 52 visit or if the duration of exposure to investigational medicinal product was at least 350 days (52 weeks \pm 2 weeks as per protocol)
- Patients who discontinued study treatment by main reason for permanent treatment discontinuation
- Patients who completed the study follow-up period as per protocol and patients who did not complete the study follow-up period as per protocol. For interim analyses, patient ongoing at the cut-off date will also be presented.
- Patients who discontinued study by main reason for study discontinuation
- Vital status (dead or alive) at last study contact

For all categories of patients (except for the screened and non-randomized categories) percentages will be calculated using the number of randomized patients as the denominator. Reasons for treatment discontinuation will be supplied in tables giving numbers and percentages by treatment arm. This summary will be provided by treatment arm.

All critical or major deviations potentially impacting efficacy analyses, randomization, and drug-dispensing irregularities, and other major or critical deviations will be summarized in tables giving numbers and percentages of deviations by treatment group.

Additionally, the analysis populations for efficacy, safety, pharmacokinetics and pharmacodynamics will be summarized in a table.

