2.4.3.1 Extent of investigational medicinal product exposure

The extent of IMP exposure will be assessed by the duration of IMP exposure.

Within each part of the study, duration of IMP exposure is defined as last dose date – first dose date + 1 day, regardless of unplanned intermittent discontinuations (see [Section 2.5.3](#) for calculation in case of missing or incomplete data).

In Part 2, the duration of exposure to GZ/SAR402671 will be calculated for both patients randomized to the GZ/SAR402671 arm and patients randomized to the placebo arm who received GZ/SAR402671 during the 104-week long term follow-up period.

The duration of exposure to GZ/SAR402671 and the duration of exposure to placebo will be summarized descriptively within each treatment arm, as a quantitative variables (number, mean, SD, median, minimum, and maximum). In addition, duration of treatment exposure will also be summarized cumulatively by numbers and percentages for each of the following categories:

- Part 1:
 - ≥ 1 day
 - ≥ 4 weeks
 - ≥ 8 weeks
 - ≥ 12 weeks
 - ≥ 24 weeks
 - ≥ 36 weeks
- Part 2:
 - ≥ 1 day
 - ≥ 4 weeks
 - ≥ 8 weeks
 - ≥ 13 weeks
 - ≥ 26 weeks
 - ≥ 39 weeks
 - ≥ 52 weeks
 - ≥ 78 weeks
 - ≥ 104 weeks
 - ≥ 130 weeks

- ≥ 156 weeks

In addition, the cumulative exposure to treatment (number of patient-years of exposure) will be summarized.

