2.4.4.1 Analysis of primary efficacy endpoint(s)

Part 1: Dose escalation phase

The primary endpoint in Part 1 is safety of each dose cohort. MDS-UPDRS in Part 1 will be analyzed for exploratory purpose (see [Section 2.4.4.3](#)).

Part 2: Treatment phase

All analyses of efficacy endpoints in Part 2 of the study will not include patients from Part 1 who are rerandomized in Part 2. Efficacy data in patients from Part 1 will be described separately, with no formal statistical testing.

Estimand

The primary estimand is the difference in mean change from baseline to Week 52 in MDS-UPDRS Part II+III score if all randomized patients had completed the treatment period, regardless of whether or not patients required initiation or intensification of levodopa/PD therapy.

A secondary estimand will be the difference in mean change from baseline to Week 52 in MDS-UPDRS Part II+III score, regardless of whether or not patients completed the treatment period or required initiation or intensification of levodopa/PD therapy.

Statistical hypotheses

Let μ_0 and μ_1 be the population means of the change from baseline to Week 52 in MDS-UPDRS Part II+III score under placebo and GZ/SAR402671, respectively. The primary hypothesis that will be tested is “H0: $\mu_0 = \mu_1$ ” versus “H1: $\mu_0 \neq \mu_1$ ”.

Primary analysis

In accordance with the primary estimand, the primary analysis will exclude data collected after premature treatment discontinuation. For patients who prematurely discontinued study treatment, any MDS-UPDRS assessed after the date of last administration of the IMP + 7 days

(corresponding to approximately 5 half-lives of GZ/SAR402671) will be excluded from the primary analysis.

Change from baseline in MDS-UPDRS Part II+III score will be analyzed using a mixed effect model with repeated measures (MMRM). All data available at Week 13, Week 26, Week 39 and Week 52 analysis time windows (as defined in Table 6) will be used in the primary analysis. For patients who prematurely discontinued study treatment, data assessed more than 7 days after the date of last administration of the IMP will be excluded from the primary analysis.

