2.4.4.2 Analyses of secondary efficacy endpoints

Part 1: Dose escalation phase

Not Applicable.

Part 2: Treatment phase

Secondary efficacy endpoints include:

- Change in PD-CRS (total score) from baseline to Week 52.
- Change in MDS-UPDRS Parts I+II+III from baseline to Week 52.
- Change in H&Y stage from baseline to Week 52.

Secondary endpoints will be analyzed using the same MMRM model as for the primary efficacy endpoint. For patients who prematurely discontinued study treatment, data collected more than 7 days after the last IMP administration will be excluded from the analysis of secondary endpoints.

Subgroup analyses

The MMRM model described as primary analysis will be repeated in each of the following subgroups as appropriate, the p-values will not be adjusted for multiplicity and will be provided for descriptive purpose only, and forest plots will be provided:

- GBA mutations (severe vs. non severe) : Severe GBA mutation subgroup will be defined using actual subgroup (not randomization stratum as per IVRS);
- Prior PD medications (yes vs. no): Prior PD medication subgroup will be defined using actual subgroup (not randomization stratum as per IVRS);
- Time since diagnosis (≤ 6 years vs > 6 years);
- Hoehn and Yahr at baseline (< 2 vs. ≥ 2);
- MoCA score at baseline (< 26 vs. ≥ 26): MoCA score subgroup will be defined using actual subgroup (not randomization stratum as per IVRS);

Unless otherwise specified (see below), for each subgroup analysis, the MMRM model will include the fixed categorical effects of treatment group, randomization strata as per IVRS, subgroup factor, time point, treatment-by-time point interaction, strata-by-time point interaction, subgroup factor-by-time point interaction, treatment-by-subgroup factor interaction, and treatment-by-subgroup-by-time point interaction, as well as the continuous fixed covariates of baseline value and baseline value-by-time point interaction. Exceptions will be made for the following subgroup analyses:

- For subgroup analyses by GBA mutation, the MMRM will not include the randomization stratum of severe GBA mutation (yes/no)
- For subgroup analyses by prior PD medication, the MMRM will not include the randomization stratum of use of levodopa/PD medication (yes/no)
- For subgroup analysis by MoCA score at baseline, the MMRM will not include the randomization stratum of MoCA score < 26 (yes/no)

Further subgroup analyses may be performed if deemed necessary for interpretation of results.

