2.5.4 Windows for time points

Data analyzed by time point (including efficacy, laboratory safety data, ECG, vital signs, quality of life and PK concentration) will be summarized using the analysis windows given in [Table 3](#), [Table 4](#), [Table 5](#), [Table 6](#) and [Table 7](#)). These analysis windows will be applicable for all analyses, and they are defined to provide more homogeneous data for time point-specific analyses.

For efficacy and quality of life endpoints, D1 will be defined as the day of randomization. For safety endpoints, D1 will be defined as the day of first IMP intake. In Part1, in case of treatment interruption of at least 7 days (corresponding to approximately 5 half-lives) between the day of first IMP intake and subsequent IMP intakes, D1 will be defined as the day of IMP resumption after treatment interruption (both for efficacy and safety endpoints).

Table 3 - Analysis windows definition for Part 1 - All endpoints except ECG and PK

Time point	Targeted study day	Analysis window in study days
Week 0 / Day 2	D2	D2
Week 0 / Day 3	D3	D3
Week 2	D15	D8 to D21
Week 4 ^a	D29	D22 to D42
Week 8	D57	D43 to D70
Week 12	D85	D71 to D98
Week 16	D113	D99 to D126
Week 20	D141	D127 to D154
Week 24	D169	D155 to D182
Week 28	D197	D183 to D210
Week 32	D225	D211 to D238
Week 36	D253	D239 to D266
Week 40	D281	D267 to D294
Week 44	D309	D295 to D322
Week 48	D337	D323 to D350
Week 52	D365	D351 to D378

^a For vital signs, any data collected between D22 and D42 will be further assigned to analysis window "Week 4 / Day 1" or "Week 4 / Day 2" as per eCRF page.

Table 4 - Analysis windows definition for Part 1 – ECG

Time point	Target study day	Analysis window
Day 1 / Pre-dose	Day 1 / Pre-dose	Before Week 0/Day 1 dose
Day 1 / 2 hours post dose	Day 1 / 2 hours post dose	1h to 2h59 after Week 0/Day 1 dose
Day 1 / 4 hours post dose	Day 1 / 4 hours post dose	3h to 4h59 post-dose after Week 0/Day 1 dose
Day 1 / 6 hours post dose	Day 1 / 6 hours post dose	5h to 8h post-dose Week 0/Day 1 dose
Week 4	D29	D22 to D42
Week 28	D197	D183 to D210

Table 5 - Analysis windows definition for Part 1 - PK concentration

Time point	Target study day	Analysis window
Day 1 / Pre-dose	Day 1 / Pre-dose	Before Week 0/Day 1 dose
Day 1 / 1 hour post dose	Day 1 / 1 hour post dose	0h50 to 1h10 after Week 0/Day 1 dose
Day 1 / 2 hours post dose	Day 1 / 2 hours post dose	1h45 to 2h15 after Week 0/Day 1 dose

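### The 7-day off-drug exclusion covers only patients who stopped prematurely, an undefined term, so a patient counted as a completer at 350 days of exposure can contribute a Week 52 score taken well beyond 7 days off drug

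*SAP*

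**What the plan says.** SAP 2.4.4.1 states the off-drug rule in these terms: "For patients who prematurely discontinued study treatment, data assessed more than 7 days after the date of last administration of the IMP" are left out. The section justifies the 7 days by pharmacokinetics: "corresponding to approximately 5 half-lives of GZ/SAR402671) will be excluded from the primary analysis". The primary estimand is the mean difference "if all randomized patients had completed the treatment period".

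SAP 2.4.4.2 repeats the condition for the secondary endpoints: "For patients who prematurely discontinued study treatment, data collected more than 7 days after the last IMP administration will be excluded".

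Neither section says who counts as having stopped prematurely. The only completion rule is in SAP 2.2. A patient has completed the 52-week period if IMP was taken until the day before the Week 52 visit, or "if the duration of exposure to investigational medicinal product was at least 350 days". Exposure runs from first to last dose, "regardless of unplanned intermittent discontinuations" (2.4.3.1).

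SAP 2.5.4, Table 6, sets the Week 52 window at D320 to D570. From D457 it overlaps Week 78, and a score there is assigned by the visit at which it was taken. Within a window, the scheduled-visit value is preferred over the value nearest the target day. On the day count: "For efficacy and quality of life endpoints, D1 will be defined as the day of randomization". All data in the Week 52 window enter the primary MMRM.

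**The concern.** SAP 1.6 says this version was written, after regulatory comments, to keep data collected after treatment discontinuation out of the primary analysis. The same version extended the Week 52 window to D570 for visits delayed by the pandemic. The two changes meet in patients who reach 350 days, stop, and are scored later. On the plain reading they are completers, so the 7-day limit never applies to them, however long they have been off drug.

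Two things are at stake. First, the wording allows more than one defensible primary dataset, and which one is used depends on how someone interprets an undefined word. Second, no planned analysis isolates the affected scores. The sensitivity analysis that adds back post-discontinuation data contains them, but so does the primary analysis, so comparing the two shows nothing about them. The secondary endpoints have the same gap, and 2.4.4.4 tests them in a confirmatory hierarchy.

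**Working it through.** **Plan's own figures.** The completion threshold is 52 × 7 − 14 = 350 days, as stated. For the sample size, a two-sample t-test with a difference of 4.06, SD 10.01 and two-sided 0.05 needs 97 per arm for 80% power, and 97 / 0.90 = 107.8, so 108 per arm, as stated. Power at 97 per arm is 80.2%.

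**Longest time off drug for a completer.** Last dose day = first dose day + exposure − 1. Time off drug = assessment day − last dose day. With exposure of exactly 350 days:

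| First dose | Last dose | Off drug at D365 | at D456 | at D570 |
|---|---|---|---|---|
| D1 | D350 | 15 | 106 | 220 |
| D2 | D351 | 14 | 105 | 219 |
| D8 | D357 | 8 | 99 | 213 |

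So 220 days is the maximum. D456 is the last day before the overlap with Week 78. The extreme is not needed to show the gap: at the D365 target, a patient who stopped on D350 is already at 15 days, more than twice the limit.

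**The one-day step.** With 349 days from D1 and the other criterion not met, the last usable score is on 349 + 7 = D356. With 350 days it is on D570. If the 7-day rule applied to everyone, a last dose on D350 would give a cut-off of D357, which is 570 − 357 = 213 days earlier.

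**Possible dilution.** The SAP does not give the share p of active-arm patients scored this way; the values below are assumptions, used only to show the range. Power is for 97 per arm and SD 10.01.

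- Effect fully lost off drug: the mean effect is 4.06 × (1 − p).
- Accrued benefit kept, as the Copy Increment from Reference analysis in 2.4.4.1 assumes after stopping. With linear accrual to 4.06 at D365 (a simplification), a D350 stopper keeps 4.06 × 350 / 365 = 3.89, and the mean effect is (1 − p) × 4.06 + p × 3.89.

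| p | Effect lost: points, power | Benefit kept: points, power |
|---|---|---|
| 0% | 4.06, 80.2% | 4.06, 80.2% |
| 5% | 3.86, 76.1% | 4.05, 80.1% |
| 10% | 3.65, 71.5% | 4.04, 79.9% |
| 20% | 3.25, 61.4% | 4.03, 79.6% |

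A share of 20% would be twice the plan's whole allowance of about 10% for early terminations and unevaluable patients (1.3.2).

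**The case against.** The best defence is that rule and estimand agree. The estimand concerns completion of the treatment period. If 2.2 counts 350 days as completion, keeping that patient's score follows the estimand as written. The disposition list in 2.2 also has a separate category for permanent treatment discontinuation, so a patient who stopped on D350 and was seen on D570 might be recorded there and excluded after all. In addition, any dilution makes the test conservative and does not inflate type I error, and the slope analysis already uses actual assessment dates.

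Much of this stands. It makes the point an ambiguity of unknown reach rather than a certain loss. It does not remove it. The SAP never says which status governs the efficacy exclusion, the 7 days rests on half-lives and not on completion status, and the slope analysis models time, not whether the patient was on drug.

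A reader might infer three stronger things that the SAP does not support:

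- That late Week 52 scores taken after a first long-term follow-up dose get in. Section 4 keeps efficacy data collected after the Week 52 visit out of the first-step analysis, and 2.3.2 places follow-up dosing after that visit. This is largely covered.
- That the patients with delayed visits are the ones affected. Nothing says they stopped drug. Those dosed until the day before a delayed visit meet the first completion criterion and are on drug when scored.
- That power falls to 61-76%. Those figures need unsourced shares and total loss of effect. The SAP's own off-drug assumption gives almost no loss.

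**Conclusion.** The gap is real on the plain reading of the SAP, and of moderate weight. It rests on taking the completion rule in 2.2 as the meaning of not premature. That is the only definition the SAP offers, and it matches the estimand's wording. On that reading, a Week 52 visit score can be 15 days off drug at the target day, 106 days at D456 and at most 220 days at D570, and still enter an analysis whose stated limit is 7. The 220 days requires dosing from D1, exactly 350 days of exposure, and a Week 52 visit on D570.

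The effect on the result cannot be sized. The number of patients is unknown, and dilution could be negligible or proportional to the share affected, depending on whether benefit persists after stopping. The case for a change is that the data rule should match the plan's own half-life criterion and be readable in only one way.

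**What to change.** In 2.4.4.1 and 2.4.4.2, drop the condition. For every patient, exclude scores taken more than 7 days after the last double-blind dose before the assessment. Counting from that dose matters: for a patient who continues into long-term follow-up, the last IMP dose overall falls after the Week 52 visit, so deleting the word prematurely would not be enough. Keep the excluded scores in the existing sensitivity analysis that includes post-discontinuation data; comparing it with the primary analysis then becomes informative about them. Add one sensitivity MMRM limiting Week 52 to D320-D456. No separate clause on follow-up doses is needed, given Section 4.

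The cost is two sentences and one model run, to be settled before unblinding. Some late Week 52 scores leave the primary model, though those patients still contribute Weeks 13 to 39. Two consequences should be stated in the text. Scores taken during a temporary interruption of more than 7 days would also be excluded. And in the Copy Increment from Reference analysis, the Week 52 scores newly missing among patients classed as completers would be imputed as missing at random, unless the SAP says otherwise. The change concerns only which data enter the models, not dosing or patient management.

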1.3.2 Part 2: Treatment phase

Approximately 216 PD patients carrying a GBA mutation in total will be randomized in a 1:1 ratio to the GZ/SAR402671 or placebo groups. A sample size of 108 patients for the GZ/SAR402671 group and 108 for the placebo group provides at least 80% power to detect a 4.06

points improvement compared to the placebo mean change in MDS-UPDRS Parts II+III score over 52 weeks. This sample size calculation assumes a 2-sided $\alpha = 0.05$, a standard deviation for the change from baseline to Week 52 in MDS-UPDRS Part II+III of 10.01 points (estimated from the Parkinson's Progression Markers Initiative [PPMI] database), and allows for an approximate 10% early terminations/unevaluable patients.

A previous study showed that a 3.25 points difference on MDS-UPDRS Part III represent the minimal clinically important difference (MCID) for detecting an improvement. It was estimated from the PPMI database that the standard deviation for change from baseline to Week 52 in MDS-UPDRS Part III was 8.01 points; therefore the MCID of 3.25 points would represent an effect size of 0.406. Since no study evaluated the MCID for MDS-UPDRS Part II+III, the same effect size of 0.406 was assumed, resulting in an estimated MCID of 4.06 points, using the standard deviation of 10.01 for change from baseline to Week 52 in MDS-UPDRS Part II+III also estimated from the PPMI database.

[figure not shown]
Of note, the approximate 27 (12 Japanese and 15 non-Japanese) early-stage PD patients carrying a GBA mutation from Part 1 may be re-randomized and participate in all of the assessments in Part 2 of this study; however, they will not contribute to the primary efficacy, safety, PK and pharmacodynamics analyses, and will be described separately.

Calculations were made using nQuery 7.0 Advisor software.

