The model will include the fixed categorical effects of treatment group (GZ/SAR402671 versus placebo), randomization strata (use of levodopa/PD medication: yes/no, MoCA score <26: yes/no and severe GBA mutation: yes/no), time point (as defined in Table 6), treatment-by-time point interaction, randomization strata-by-time point interaction as well as the continuous fixed covariates of baseline MDS-UPDRS Part II+III score and the baseline-by-time point interaction.

This model will be run using SAS Mixed procedure with an unstructured correlation matrix to model the within-patient errors. Parameters will be estimated using restricted maximum likelihood method. Denominator degrees of freedom will be estimated using Kenward-Roger approximation. This model will provide baseline adjusted least-squares means estimates at Week 52 for both treatment groups with their corresponding standard errors (SEs) and 95% confidence intervals (CI). The difference in baseline adjusted least-squares means will be used to compare the GZ/SAR402671 group to the placebo group, at the 2-sided 0.05 level.

Within group least-squares means and standard errors will be calculated using weights equal to the observed proportion of patients in strata variable levels in the study population (i.e. “population weight”) rather than equal weights. Population weights are considered more appropriate than equal coefficients due to expected unbalances in the study population between levels of the randomization stratification factors.

In addition, the relative reduction versus placebo will be calculated as:

$$\text{Relative reduction (\%)} = \left(1 - \frac{\text{LS mean change at Week 52 in GZ/SAR402671 arm}}{\text{LS mean change at Week 52 in placebo arm}} \right) \times 100$$

Relative reduction will be presented with 95% confidence interval using Fieller method. This confidence interval will be calculated provided a significant change is observed in the placebo arm at the 0.05 level. In addition, the posterior probability that GZ/SAR402671 achieves a relative reduction by at least 25% and 50% will be calculated using samples from the asymptotic distribution of LS means from the two treatment arms.

Sensitivity analysis including data collected after treatment discontinuation

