A sensitivity analysis will estimate the difference in mean change from baseline to Week 52 in MDS-UPDRS Part II+III score regardless of whether or not patients completed the treatment period. In this sensitivity analysis, MDS-UPDRS assessed more than 7 days after the last IMP

administration will be included in the analysis. The MMRM model described as primary analysis will be repeated after inclusion of these data.

Sensitivity analysis with slope-based analysis

The rate of change in MDS-UPDRS Part II+III score from baseline to Week 52 will be estimated using a slope-based analysis assuming linear change from baseline to Week 52. A linear mixed effect model will be fitted, which will include the fixed effect of treatment group (GZ/SAR402671 versus placebo), randomization strata (use of levodopa/PD medication: yes/no, MoCA score <26: yes/no and severe GBA mutation: yes/no), time in years from baseline (as continuous variable), treatment*time interaction and randomization strata*time interaction, and will include random intercept and slope. Time (in years) will be calculated as (date of assessment – date of randomization + 1) / 365.25.

Within group mean slope will be obtained from the linear mixed effect and difference in slopes will be presented with the 95% confidence intervals. P-value of the comparison of slopes will be presented for descriptive purpose only.

Relative reduction in slope will be presented with 95% confidence interval. The posterior probability that GZ/SAR402671 achieves a relative reduction in slope by at least 0%, 25% and 50% will be calculated.

[figure not shown]
Sensitivity analysis exploring alternative approach regarding missing data

The MMRM model relies on the “missing-at-random” (MAR) assumption. As the possibility for a not-missing-at-random (NMAR) missingness mechanism cannot be excluded, a sensitivity analysis to explore the impact of nonignorable missingness on the primary efficacy analysis will be conducted.

The sensitivity analysis will be based on a pattern-mixture model. Multiple imputations will be generated using a “Copy Increment from Reference” (2) method. Assumptions underlying this method are the following:

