- Excluding any MDS-UPDRS assessed less than 6 hours after intake of PD medication (irrespective of clinical state)
- Excluding any MDS-UPDRS assessed less than 12 hours after intake of PD medication and for which the clinical state was recorded as “ON”.
- Excluding any MDS-UPDRS assessed less than 6 hours after intake of PD medication and for which the clinical state was recorded as “ON”.

The MMRM model described as primary analysis will be repeated after exclusion of these data.

Sensitivity analyses assessing randomization strata

A sensitivity analysis will estimate the difference in mean change from baseline to Week 52 in MDS-UPDRS Part II+III score after including the actual strata derived from data instead of the strata recorded in IVRS (use of levodopa/PD medication: yes/no, MoCA score <26: yes/no and severe GBA mutation: yes/no). The purpose of this analysis will be to assess the impact of discrepancies observed between the strata recorded in the IVRS and the ones derived from data. The MMRM model described as primary analysis will be repeated after including the actual strata.

Secondary analysis

A secondary analysis will describe the number and percentage of patients with MDS-UPDRS Part II+III score improvement, no change or worsening at Week 52 based on minimal clinically important difference threshold values in patients with Hoehn&Yahr 1&2 (5):

- Improvement will be defined as change in MDS-UPDRS Part II+III ≤ -4.3
- Worsening will be defined as change in MDS-UPDRS Part II+III ≥ 3.9
- No change will be defined as change in MDS-UPDRS Part II+III > -4.3 and < 3.9

Patients without any available assessment at Week 52 will be considered as worsened.

Subgroup analyses

The MMRM model described as primary analysis will be repeated in each of the following subgroups as appropriate, the p-values will not be adjusted for multiplicity and will be provided for descriptive purpose only, and forest plots will be provided:

- Sex (Male vs. Female);
- Age (≤ 60 vs. > 60);
- GBA mutations (severe vs. non severe) : Severe GBA mutation subgroup will be defined using actual subgroup (not randomization stratum as per IVRS);

- Prior PD medications (yes vs. no): Prior PD medication subgroup will be defined using actual subgroup (not randomization stratum as per IVRS);
- Time since onset of symptoms (≤ 6 years vs > 6 years);
- Time since diagnosis (≤ 6 years vs > 6 years);
- MDS-UPDRS Part II+III at baseline (≤ 35 vs. > 35);

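### The posterior probabilities of a relative reduction carry no condition on the sign of the placebo mean, so negative placebo draws are scored the wrong way round

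*SAP*

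**What the plan says.** In SAP section 2.4.4.1, under Primary analysis, "the relative reduction versus placebo will be calculated as" one minus the LS mean change at Week 52 on drug divided by that on placebo, times 100. A Fieller confidence interval follows, with a safeguard: "This confidence interval will be calculated provided a significant change is observed in the placebo arm at the 0.05 level". The next sentence adds a separate output: "the posterior probability that GZ/SAR402671 achieves a relative reduction by at least 25% and 50% will be calculated using samples from the asymptotic distribution" of the two arms' LS means. It has no condition on the placebo arm and no rule for a sampled placebo mean at or below zero.

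Under the slope-based sensitivity analysis in the same section, a relative reduction in slope is planned with a 95% confidence interval, and "The posterior probability that GZ/SAR402671 achieves a relative reduction in slope by at least 0%, 25% and 50% will be calculated". Here neither the interval nor the probabilities are conditional on the placebo slope.

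The direction of the scale is clear from the responder analysis in the same section: "Worsening will be defined as change in MDS-UPDRS Part II+III ≥ 3.9". A positive change is a worsening.

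**The concern.** A relative reduction has its intended meaning only if the denominator, the placebo change, is a worsening. The plan guards the Fieller interval against a doubtful denominator, but not the probabilities computed from the same ratio. If the placebo change turned out not to be significant, the interval would be withheld and the probability would still be printed.

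A draw with a negative placebo mean does more than add noise, because it reverses the comparison. The printed probability could then suggest some chance of a 25% or 50% slowing when the data favour placebo, or almost none when they favour the drug. The safeguard also asks only for a significant change, so a significant placebo improvement would satisfy it.

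**Working it through.** **Inputs.** SAP section 1.3.2 gives "a standard deviation for the change from baseline to Week 52 in MDS-UPDRS Part II+III of 10.01 points", "A sample size of 108 patients for the GZ/SAR402671 group and 108 for the placebo group", and states that the calculation "allows for an approximate 10% early terminations/unevaluable patients". The target difference is 4.06 points at 80% power and two-sided 0.05. No expected placebo change is stated, so a range is assumed below.

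**The plan's sample size first.** n per arm = 2 × (1.96 + 0.842)² × (10.01/4.06)² = 95.4, rounded up to 96. Then 96/0.9 = 106.7, so 107 per arm and 214 in total, in line with the stated 216. With 108 × 0.9 ≈ 97 evaluable per arm, power is 80.6% (normal) or 80.2% (t).

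**Algebra.** Let P and T be the sampled placebo and drug means and c the threshold. The event is 1 − T/P ≥ c, that is T/P ≤ 1 − c.
- If P > 0, this is T ≤ (1 − c)P, as intended.
- If P < 0, this is T ≥ (1 − c)P. For c = 0.25 or 0.50, (1 − c)P lies above P, so every such success has T > P: the drug is worse than placebo in that draw.
- If P < 0 and T < P (drug better), then T/P > 1, the relative reduction is negative, and the draw is a failure.

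**Size.** SE per arm = 10.01/√97 = 1.016. For placebo +1 and drug +3:
- Share of negative placebo draws: Φ(−1/1.016) ≈ 0.16. Nearly all of them count as success.
- Intended event at 25%: T − 0.75P has mean 2.25 and SD 1.016 × √(1 + 0.75²) = 1.27, so the probability is Φ(−1.77) ≈ 0.04.
- Printed total ≈ 0.16 + 0.04 = 0.20.

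Two million independent normal draws per arm give the following. Each pair is the 25% / 50% threshold.

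| Placebo, drug | P(placebo draw < 0) | As written | Positive placebo draw required | P(drug better) |
|---|---|---|---|---|
| −2, −4 | 0.975 | 0.049 / 0.029 | 0.025 / 0.025 | 0.918 |
| −2, +2 | 0.975 | 0.975 / 0.973 | 0.001 / 0.001 | 0.003 |
| −1, +1 | 0.838 | 0.847 / 0.822 | 0.046 / 0.039 | 0.082 |
| 0, +4 | 0.500 | 0.500 / 0.500 | 0.001 / 0.000 | 0.003 |
| +1, +3 | 0.162 | 0.200 / 0.176 | 0.038 / 0.014 | 0.082 |
| +2, +6 | 0.025 | 0.025 / 0.025 | 0.000 / 0.000 | 0.003 |
| +3, +3 | 0.002 | 0.279 / 0.095 | 0.277 / 0.093 | 0.500 |
| +4, +4 | 0.000 | 0.215 / 0.039 | 0.215 / 0.039 | 0.500 |

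For placebo +0.5 and drug +2.5, the 25% figure is 0.36 as written against 0.05.

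The spurious part cannot exceed the share of negative placebo draws. Placebo worsening is just significant at 1.96 × 1.016 = 1.99 points, where that share is 2.5%.

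**Slope.** The SAP gives no variance for the slopes, so no size can be derived directly. Using the Week 52 means as a stand-in, the 0% threshold at placebo +1 and drug +3 gives 0.24 as written, although the drug is better in only 0.08 of draws.

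**The existing gate.** Placebo −2.5 and drug 0 meets a two-sided significance condition on placebo (2.5/1.016 = 2.46). As written, P(at least 25%) is then 0.93, although the estimate favours placebo by 2.5 points.

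**The case against.** The strongest case against is about reach. The SAP itself describes Parkinson's disease as progressive and expects treatment to slow it. A drug that only slows progression can gain 4.06 points only if placebo worsens by at least that much, and at placebo +4 the error vanishes. Assessments are planned in the OFF state, which limits how far added PD medication can pull the placebo change towards zero. The probabilities have no decision threshold. Both LS means, their intervals and their difference are reported beside them, so a reader would see that the drug did worse.

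The magnitudes are also approximate. If covariate adjustment removed 20% of the variance (an assumption), the 0.20 would be about 0.16. With a correlation of 0.2 between arm means (also assumed), it would be 0.19 against 0.02.

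All of this limits the size, but none of it removes the sign reversal. The primary estimand keeps data after PD therapy is started or intensified, and the Fieller condition shows that the plan allows for a placebo change that is not significant. It does not show that the plan expects one.

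A reader might infer that the probabilities are always biased upward, or that every negative placebo draw scores a harmful drug as a success. Neither follows. At placebo −2 and drug −4 the drug is better in 92% of draws, yet the planned 25% probability is 0.05. Where P < T < 0, both arms improve and the drug is merely worse than placebo.

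**Conclusion.** The point holds as a defect in a supplementary output. Followed literally, section 2.4.4.1 gives wrong probabilities whenever a material share of placebo draws is negative, and the error can go in either direction. It is large for a placebo change near or below zero, at most about 2.5 percentage points at +2, and negligible from about +3. The sign argument needs no assumption about the data. The sizes rest on the plan's SD, 97 evaluable patients per arm, independent unadjusted draws and assumed placebo means.

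A reader might go further and conclude that the trial's efficacy inference is compromised. The SAP does not support that: the confirmatory test is the LS mean difference at the two-sided 0.05 level, and the testing hierarchy does not use these probabilities. A reader might also think that extending the Fieller condition would be enough. As worded it would not be, because it admits significant placebo improvement.

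**What to change.** Define the event without the ratio. Count a draw only if the placebo mean is above zero and the drug mean is at most 0.75 times the placebo mean (0.50 for the 50% threshold, 1.00 for the 0% threshold on the slope). Draw the two means, or slopes, jointly with their model covariance.

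Report these probabilities, and the relative-reduction intervals for both the LS means and the slopes, only when the placebo arm shows significant worsening, meaning a significant positive change or slope. Otherwise report only the difference in means or slopes.

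The cost is about one line of code and one SAP sentence, carried through to the slope analysis and settled before unblinding. No data collection, sample size or primary analysis changes.
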